Compared to IV administration, IM administration produces lower peaks, longer half-life, and higher volumes of distribution for AS, as well as delayed peaks for DHA. For example, AS half-life following in IV administration is less than 15 minutes on average, compared to 25.2 to 48.2 minutes with IM administration.²⁹ Other parameters – in including DHA half-life, volume of distribution, and clearance rates following IM administration resembled the values recorded after IV administration in multiple studies, due to the high bioavailability, assessed by exposure to DHA, associated with IM AS administration (>86%).²⁹ The AUC of AS following IM administration of 120 mg AS in adults ranged between 856³⁵ - 999³¹ng*hr/ml in those with malaria. The AUC of DHA following IM administration of 120 mg of AS in adults with malaria was 2474ng*hr/ml in one study.³¹

308 309 310

311

312

313

314315

316

317

318

319

320

321 322

323 324

325

326

327

328 329

330

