When AS is administered orally, DHA peak concentrations (Cmax), AUC, and half-life averages are all notably higher than comparable AS parameters. The average time to DHA Cmax and halflife following oral AS administration (200 mg/day) are 2 hours, and 0.5-1.5 hours, respectively, compared to one hour and 20-45 minutes, respectively, for AS.²⁹ While a similar pattern is seen following IV and IM administration, namely, elevated levels of DHA half-life and AUC compared to AS, the difference are notable following oral administration. Also, while oral administration of AS results in a higher DHA Cmax compared to AS, IV and IM administration result in a notably higher AS Cmax than DHA Cmax. Morris et al (2011) points out that the variations observed following oral administration are most likely attributed to AS functioning as a "pro-drug" for DHA when ingested orally and in response to "first-pass or systemic metabolism."²⁹ Essentially, when AS is taken orally, it is converted to DHA at a greater extent than when it is taken intravenously or intramuscularly. The AUC of AS and DHA in a study of healthy adult volunteers taking 200mg AS daily for 5 days was 67 ng*hr/ml and 1158 ng*hr/ml for AS & DHA, respectively, on Day 1, and 60 ng*hr/ml and 1300 ng*hr/ml for AS & DHA, respectively, on Day 5.36 Similar Cmax parameters for AS were 67 ng/ml and 58 ng/ml on Day 1 and 5, respectively, and a pooled DHA Cmax of 654 ng/ml, demonstrating the absence of timedependent artesunate pharmacokinetics in healthy subjects during 5-day oral administration of 200 mg artesunate.³⁶ The AUC of AS following oral administration of 200 mg AS in adults ranged between 60-67ng*hr/ml in healthy volunteers³⁷ and 310ng*hr/ml in those with malaria.³⁸ The AUC of DHA following oral administration of 200 mg of AS in adults ranged from 1158-1331 ng*hr/ml ^{37,39}in healthy volunteers to 3027ng*hr/ml in those with malaria. ³⁸

351

352

363

364

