331 Rectal AS administration yields pharmacokinetic results similar to those obtained from oral 332 administration, with the exception of delayed AS Cmax and longer AS half-life. Compared to IV 333 administration, expectedly, both AS absorption and elimination are prolonged following rectal administration. Following rectal administration of AS, Tmax average between 0.58-1.43 hours. 334 with a half-life between 0.9-.95 hours.²⁹ These averages are based on three different studies: two 335 336 studies containing pediatric patients with uncomplicated falciparum malaria (10 - 20mg/Kg 337 dosing)^{40,41} and one study containing healthy Malaysian adults (200 mg rectal suppository, 338 ~4mg/Kg dosing). 42 Following rectal dosing of a one-time 200 mg AS suppository in healthy 339 adults (similar to our planned dosing), a Cmax, Tmax, half-life and AUC of 448.5 ng/ml, 1.43 340 hours, 0.95 hours, and 796 ng*hr/ml of AS were observed, and Cmax, Tmax, half-life and AUC 341 of 385.6 ng/ml, 1.80 hours, 1.21 hours, and 965 ng*hr/ml respectively of DHA were observed in 342 healthy adults. 42 No data are available on rectal PK in adults with malaria as this route of 343 administration is not used to treat malaria in adults. The longer half-life of AS following rectal 344 dosing (average 0.9-0.95 hrs) compared to IM (average 25.2 – 48.2 minutes), or IV (average less than 5 minutes) may reflect absorption rate-limited elimination of AS.²⁹ As is expected given 345 346 that rectal AS administration avoids by-pass metabolism, the discrepancy in AS and DHA AUC 347 values (796 ng*hr/ml and 965 ng*hr/ml, respectively), is not as striking with rectal, as compared with oral administration of AS (119 ng*hr/ml and 1331 ng*hr/ml, respectively). ²⁹ Similar to oral 348 349 administration, both DHA Tmax and half-life values were higher than that of AS following rectal 350 administration.29

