4.5.2 Data Analysis Plans

- 1117 **Primary Outcome:** Plasma concentration versus time curve (AUC) of dihydroartemisinin
- 1118 (DHA) following five consecutive days of self-administration of 200mg Artesunate vaginal
- inserts (pessaries) among healthy women in Kenya.
- 1120 Primary Endpoint: Mean DHA AUC (ng*hr/ml) with standard deviation on Day 5
- 1121 Statistical analysis: Mean DHA AUC will be compared to historical studies after IV, oral and
- rectal administration among adults following similar dosing. Results will be analyzed using the
- student's t-test for one-sample observation and a p-value of 0.05 will be considered statistically
- 1124 significant.

1125 1126

Secondary Outcomes

- 1127 1.Plasma AUC of Artesunate following 5-day self-administration of 200mg Artesunate vaginal
- inserts (pessaries)
- 1129 Endpoint: Mean artesunate AUC (ng*hr/ml) with standard deviation on Day 5
- 1130 Statistical analysis: Mean artesunate AUC (ng*hr/ml) will be compared to historical studies after
- 1131 IV, oral and rectal administration among adults following similar dosing. Results will be
- analyzed using the student's t-test for one-sample observation and a p-value of 0.05 considered
- statistically significant.

1134

- 2. Maximum concentration of Artesunate (Cmax) following 5-day self-administration of 200mg
- 1136 Artesunate vaginal inserts (pessaries)
- 1137 Endpoint: Mean artesunate Cmax (ng/ml) with standard deviation on Day 5
- 1138 Statistical analysis: Mean artesunate Cmax (ng/ml) will be compared to historical studies after
- 1139 IV, oral, and rectal administration among adults following similar dosing. Results will be
- analyzed using the student's t-test for one-sample observation, and a p-value of 0.05 considered
- statistically significant.

- 3. Maximum concentration of DHA (Cmax) following 5-day self-administration of 200mg
- 1144 Artesunate vaginal inserts (pessaries)
- 1145 Endpoint: Mean DHA Cmax (ng/ml) with standard deviation on Day 5
- 1146 Statistical analysis: Mean DHA Cmax (ng/ml) will be compared to historical studies after IV,
- oral and rectal administration among adults following similar dosing. Results will be analyzed

PI: [name] UNIVERSITY OF NORTH CAROLINA Version 1.0 April 25, 2023

- 1148 using the student's t-test for one-sample observation and a p-value of 0.05 considered statistically 1149 significant.

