- 1151 4. Time to maximum concentration (Tmax) of Artesunate following 5-day self-administration of
- 1152 200mg Artesunate vaginal inserts (pessaries)
- 1153 Endpoint: Mean Artesunate Tmax (mins) with standard deviation on Day 5
- 1154 Statistical analysis: Mean artesunate Tmax (mins) will be compared to historical studies after IV,
- 1155 oral, and rectal administration among adults following similar dosing. Results will be analyzed
- 1156 using the Mann-Whitney U-test for nonparametric data, and a p-value of 0.05 considered
- 1157 statistically significant.
- 1159 5. Time to maximum concentration (Tmax) of DHA following 5-day self-administration of
- 1160 200mg Artesunate vaginal inserts (pessaries)
- 1161 Endpoint: Mean DHA Tmax (mins) with standard deviation on Day 5
- Statistical analysis: Mean DHA Tmax (mins) will be compared to historical studies after IV, oral 1162
- 1163 and rectal administration among adults following similar dosing. Results will be analyzed using
- 1164 the Mann-Whitney U-test for nonparametric data and a p-value of 0.05 considered statistically
- 1165 significant. 1166

1150

1158

- 1167 6. Artesunate half-life (t_{1/2}) following 5-day self-administration of 200mg Artesunate vaginal
- 1168 inserts (pessaries)
- 1169 Endpoint: Mean Artesunate half-life $(t_{1/2})$ (mins) with standard deviation on Day 5
- 1170 Statistical analysis: Mean Artesunate half-life $(t_{1/2})$ (mins) will be compared to historical studies
- 1171 after IV, oral and rectal administration among adults following similar dosing. Results will be
- analyzed using the Mann-Whitney U-test for nonparametric data and a p-value of 0.05 1172
- 1173 considered statistically significant.
- 1175 7. DHA half-life $(t_{1/2})$ following 5-day self-administration of 200mg Artesunate vaginal inserts
- 1176 (pessaries)

1174

1182

- 1177 Endpoint: Mean DHA half-life (mins) with standard deviation on Day 5
- 1178 Statistical analysis: Mean DHA half-life (t_{1/2}) (mins) will be compared to historical studies after
- 1179 IV, oral and rectal administration among adults following similar dosing. Results will be
- 1180 analyzed using the Mann-Whitney U-test for nonparametric data and a p-value of 0.05
- 1181 considered statistically significant.
- 1183 8. Apparent clearance of Artesunate (AS) following 5-day self-administration of 200mg
- 1184 Artesunate vaginal inserts (pessaries)
- Endpoint: Mean Artesunate clearance (L/Kg/hr) with standard deviation on Day 5 1185

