- 1186 Statistical analysis: Mean Artesunate clearance (L/Kg/hr) will be compared to historical studies
- 1187 after IV, oral and rectal administration among adults following similar dosing. Results will be
- 1188 analyzed using the students t-test for one-sample observation and a p-value of 0.05 considered
- 1189 statistically significant.
- 1191 9. Apparent clearance of DHA following 5-day self-administration of 200mg Artesunate vaginal
- 1192 inserts (pessaries)
- 1193 Endpoint: Mean DHA clearance (L/Kg/hr) with standard deviation on Day 5

PI: [name] UNIVERSITY Version 1.0

- 1194 Statistical analysis: Mean DHA clearance (L/Kg/hr) will be compared to historical studies after
- 1195 IV, oral and rectal administration among adults following similar dosing. Results will be
- analyzed using the students t-test for one-sample observation and a p-value of 0.05 considered

statistically significant.

1198

- 1199 10. Volume of distribution of Artesunate (AS) following 5-day self-administration of 200mg 1200 Artesunate vaginal inserts (pessaries)
- 1201 Endpoint: Mean Artesunate volume of distribution (L/Kg) with standard deviation on Day 5
- 1202 Statistical analysis: Mean Artesunate volume of distribution (L/Kg) will be compared to
- 1203 historical studies after IV, oral and rectal administration among adults following similar dosing.
- Results will be analyzed using the students t-test for one-sample observation and a p-value of
- 1205 0.05 considered statistically significant.

1206

- 1207 11. Volume of distribution of DHA following 5-day self-administration of 200mg Artesunate vaginal inserts (pessaries)
- 1209 Endpoint: Mean DHA volume of distribution (L/Kg) with standard deviation on Day 5
- 1210 Statistical analysis: Mean DHA volume of distribution (L/Kg) will be compared to historical
- studies after IV, oral and rectal administration among adults following similar dosing. Results
- will be analyzed using the students t-test for one-sample observation and a p-value of 0.05
- 1213 considered statistically significant.

1214

- 1215 12. Safety of 5-day course of self-administrated 200mg Artesunate vaginal inserts (pessaries) 1216 among health women in Kenya
- 1217 Endpoint: Type, frequency, severity, and duration of reported and observed adverse events (AEs)
- using the U.S National Cancer Institute Common Terminology Criteria for Adverse Events, v5.0

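### The historical comparisons treat unnamed, estimated means as exact in eight one-sample t-tests, and the four Mann-Whitney tests have no second sample specified

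*Combined protocol and SAP*

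**What the plan says.** Section 4.5.2 compares all twelve PK endpoints with historical studies in adults given similar doses by the IV, oral and rectal routes.

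- **Eight endpoints** use a one-sample t-test: DHA AUC (primary), artesunate AUC, and Cmax, apparent clearance and volume of distribution of both analytes. For the primary endpoint the wording is "student's t-test for one-sample observation and a p-value of 0.05 will be considered statistically" significant. For clearance it is "Mean Artesunate clearance (L/Kg/hr) will be compared to historical studies", followed by the same test.
- **Four endpoints**, Tmax and half-life of both analytes, are analysed "using the Mann-Whitney U-test for nonparametric data, and a p-value of 0.05 considered" significant.

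The section names no study, reference value, reference SD or n, rule for choosing between studies of one route, or sidedness. The only null hypothesis stated (Section 2.1) concerns change from baseline, so it supplies no value for these tests.

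Section 1.3 quotes several DHA AUCs (ng*hr/ml) that could serve:

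| Route and dose | Population | DHA AUC |
|---|---|---|
| Rectal 200 mg, single dose | healthy | 965 |
| Oral 200 mg | healthy | 1158 (Day 1), 1300 (Day 5), 1331 |
| Oral 200 mg | malaria | 3027 |
| IV 120 mg | healthy | 1850 |
| IV 120 mg | malaria | 1845-2377 |

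None comes with an SD or n.

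**The concern.** A one-sample t-test carries only the sampling error of the twelve trial participants. A mean taken from a historical PK study has sampling error of its own, often from a group no larger than this one. If that error is ignored, the test rejects too often when the true means are equal.

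Because no reference is fixed, it can also be picked after the concentrations are known, and candidates within one route differ enough to move a result across 0.05.

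A Mann-Whitney test ranks individual values from two groups. This is a single-arm study, and no second group is specified.

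At stake are the statements that vaginal exposure is or is not significantly different from oral, rectal or IV exposure. These are the only inferential results planned for the primary endpoint.

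**Working it through.** **Inputs.** n=12 evaluable (Section 4.5.1), so 11 degrees of freedom. Nominal level 0.05, taken as two-sided, with critical value 2.201. Historical sample size m and SD ratio r (historical SD / trial SD) are assumptions. As a guide, the two studies whose size is given (Section 1.4) had 6 to 10 subjects per group. Normal data are assumed. The plan offers no figure to reproduce: n=12 rests on custom in PK studies, not on a power calculation.

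**1. Real error rate.** With equal true means, the difference between the trial mean and the historical mean has variance (σ²/12)(1 + 12r²/m). The one-sample statistic allows only for σ²/12. Hence

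real error = 2·P(t₁₁ > 2.201 / √(1 + 12r²/m)).

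| m | √(1+12/m) | 2.201 / that | error, r=1 | error, r=0.5 |
|---|---|---|---|---|
| 6 | 1.732 | 1.271 | 0.230 | 0.100 |
| 12 | 1.414 | 1.556 | 0.148 | 0.075 |
| 20 | 1.265 | 1.740 | 0.110 | 0.065 |
| 30 | 1.183 | 1.860 | 0.090 | 0.060 |

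With r=2 and m=12 it is 0.346. As m grows it returns to 0.05, which is the fixed-benchmark case. Simulation at m=6, 12 and 30 agrees with the formula, and a Welch test using the historical mean, SD and n stays at 0.048-0.054 for r=0.5, 1 and 2.

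**2. Choice of reference within one route.** Assume an observed DHA AUC mean of 950 with SD 475. The standard error is 475/√12 = 137.1.

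| Healthy oral 200 mg reference | t | p |
|---|---|---|
| 1158 | 208/137.1 = 1.52 | 0.16 |
| 1300 | 350/137.1 = 2.55 | 0.027 |
| 1331 | 381/137.1 = 2.78 | 0.018 |

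The conclusion against oral dosing depends on which of three quoted values is used. Now let the 1300 reference carry its own error, assuming 12 subjects and the same 50% CV (SD 650). The standard error becomes √(137.1² + 650²/12) = 232.4, t = 350/232.4 = 1.51, and the Welch p is 0.15 instead of 0.027.

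**3. Where the two tests disagree.** Assume a CV of 60% in both groups on the raw scale. The one-sample test becomes significant when 1 − x > 2.201 × 0.6x/√12 = 0.381x, that is, when the observed mean is below 1/1.381 = 72% of the reference. Welch becomes significant only below 37% (m=6), 58% (m=12) or 67% (m=30). The tests disagree between those limits. On the log scale the zone is narrower: about 54-70% for m=6 and 63-70% for m=12.

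**4. IV values.** The quoted IV figures are at 120 mg and no scaling rule is given. The healthy-adult value is 1850 as quoted, or 1850 × 200/120 = 3083 if exposure is assumed proportional to dose.

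**5. Mann-Whitney.** If a single published value stood in for the second sample, the smallest exact two-sided p with twelve observations is 2/13 = 0.154, so 0.05 could not be reached.

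**6. Clearance and volume.** The objectives (Section 2.2) define these as CL/F and V/F. With identical disposition, vaginal CL/F divided by IV clearance equals 1/F(vaginal), and vaginal CL/F divided by oral CL/F equals F(oral)/F(vaginal). A difference from any route therefore mixes bioavailability with clearance or volume.

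**The case against.** Five points can fairly be made for the plan.

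- **All three routes are planned.** Different p-values against rectal and oral references would answer different questions, so that contrast does not show a movable reference. This stands, and is why the example above stays within the oral route. For the rectal route Section 1.3 quotes only one adult DHA AUC, "of 385.6 ng/ml, 1.80 hours, 1.21 hours, and 965 ng*hr/ml respectively of DHA were observed in" healthy adults, and describes that dosing as close to the study's own.
- **A one-sample test is exact against a benchmark fixed in advance.** True, but the plan fixes none.
- **The historical n and SD are unseen.** True. A reader might take 23% as the test's error rate. The documents do not support that: it needs six historical subjects and equal SDs. What does not depend on the assumptions is the direction.
- **Exposure is expected to be very low** (Sections 1.6 and 5.4), so the tests would mostly agree. With an assumed mean of 200 and CV of 30-50%, the one-sample p is below 0.0001 against every DHA AUC listed. This limits the harm, but low exposure is what the study sets out to confirm.
- **Individual historical data could be obtained.** A reader might infer that the Mann-Whitney tests are impossible. The supportable statement is that their second sample is not specified, and the 0.154 floor applies only if one published value is used.

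A reader might also infer that the oral malaria value is a live reference, since the range runs from 1158-1331 "in healthy volunteers to 3027ng*hr/ml in those with malaria" and the similar-dosing filter does not say healthy. That is strained: the outcome is defined in healthy women, malaria-positive women are excluded, and Section 1.4 discusses higher DHA exposure in malaria.

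**Conclusion.** The concern holds in this form: eight one-sample t-tests, including the primary, ignore the sampling error of a reference that is not fixed for any route, and four Mann-Whitney tests lack a specified second sample.

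Under equal true means and equal SDs, the real two-sided error is about 9-23% for 30 down to 6 historical subjects. It is 6-10% if the historical SD is half the trial's, and higher if it is larger. These sizes rest on assumed historical n and SD and on normal data.

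A reader might infer that the primary result itself is invalid. The documents do not support that. The mean AUC with SD is unaffected, no decision rule uses these p-values, and the harm is confined to significance claims, mainly where vaginal exposure lies near a reference value. The plan should be corrected on this point before the samples are assayed.

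**What to change.** Before assay, amend Section 4.5.2 as follows.

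1. Name one reference study per route, or one primary reference, with its mean, SD, n, dose and population, and justify the choice. Candidates in Section 1.3 are the single-dose 200 mg rectal study (965) and the 5-day 200 mg oral study (Day 5, 1300), which matches the Day 5 sampling here.
2. For AUC and Cmax, replace the one-sample t-tests with a Welch difference and 95% CI from summary statistics. If a ratio is preferred, take its CI from log-scale summaries or a Fieller or delta method, since it does not follow from a raw-scale Welch test.
3. If a reference reports no usable SD or n, compare descriptively, or state that the value is treated as a fixed benchmark.
4. Label any scaling of the 120 mg IV values to 200 mg as an assumption.
5. Report Tmax and half-life as median and range beside the published values, unless individual historical data are obtained.
6. Present CL/F and V/F descriptively against every route, noting that each non-IV route carries its own bioavailability and IV carries none.
7. State that Welch corrects only for sampling error in the reference; differences in population, assay and route remain.

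The cost is revised wording, one reference table, and a search of the cited papers for SD and n, which may not always be reported in usable form. No new participants, visits or samples are needed. The downside is wider intervals and fewer p-values.

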1.3 Summary of Artesunate Pharmacokinetics

273274275

276

277

278279

280

281

282

283

284

285

The pharmacokinetics (PK) measures of artesunate (AS) and dihydroartemisinin (DHA) following intravenous (IV), intramuscular (IM), oral and rectal administration have been well described. These PK parameters include maximum concentration of the drug in the blood (Cmax), time to maximum concentration Cmax (Tmax), apparent clearance (CL/F) - the drug concentration in the body in proportion to the rate of elimination, volume of distribution (V/F), the area under the plasma concentration versus time curve (AUC) which expresses the total amount of the drug in systemic circulation after administration, and half-life (t_{1/2}). Intravenous administration of AS produces quickly produces high maximum concentrations (Cmax) of AS, higher than any other method of administration. One example of this can be seen in a study of adults with uncomplicated malaria which compared AS and DHA levels following IV and IM administration. Cmax values for AS when administered intravenously reached over 16.000ng/mL

PI: [name] Version 1.0

while only reaching around 884ng/mL when administered intramuscularly. 30 Similarly, the 286 287 maximum concentration (Cmax) of AS and DHA peak quickly following IV administration, 288 followed by a rapid decline. The average half-life of AS following IV administration of less than 289 fifteen minutes in multiple studies, with an observed clearance range of 2-3 L/kg/hr and a volume range of 0.1-0.3 L/kg.²⁹ The hydrolysis of AS into DHA following IV administration is 290 291 similarly quick, with maximum DHA levels reached soon after IV AS administration. The Tmax 292 for DHA after IV administration was consistently less than 25 minutes according to the observed 293 studies with DHA clearance averaging between 0.5-1.5 L/kg/hr and volume averaging between 0.5-1.0 L/kg.²⁹ The AUC of AS following IV administration of 120 mg AS in adults ranged 294 between 876ng*hr/ml in healthy volunteers³¹ and 1038 - 1269ng*hr/ml in those with malaria.³² 295 296 The AUC of DHA following IV administration of 120 mg AS in adults ranged from 1850 ng*hr/ml in healthy volunteers³³ to 1845-2377ng*hr/ml in those with malaria.³⁴ 297

298 299

300

301

302 303

304

305

306

307

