- 8. To determine the apparent clearance (CL/F) of Artesunate (AS) following five consecutive days of self-administration of 200mg Artesunate vaginal inserts (pessaries) among healthy women in Kenya
- To determine the apparent clearance (CL/F) of dihydroartemisinin (DHA) following five consecutive days of self-administration of 200mg Artesunate vaginal inserts (pessaries) among healthy women in Kenya
- 10. To determine the volume of distribution (V/F) of Artesunate (AS) following five consecutive days of self-administration of 200mg Artesunate vaginal inserts (pessaries) among healthy women in Kenya
- 11. To determine the volume of distribution (V/F) of dihydroartemisinin (DHA) following five consecutive days of self-administration of 200mg Artesunate vaginal inserts (pessaries) among healthy women in Kenya
- 12. To investigate the safety of 5-day course of self-administered intravaginal artesunate vaginal inserts (pessary) in women in Kenya

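### Apparent clearance and volume after a vaginal dose (CL/F, V/F) are tested against IV clearance and volume, so a difference from IV would reflect bioavailability, not clearance or volume

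*Combined protocol and SAP*

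**What the plan says.** Section 2.2 defines the parameters correctly as apparent quantities, for example "To determine the apparent clearance (CL/F) of Artesunate (AS) following five consecutive days", and does the same for V/F.

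In section 4.5.2, outcomes 8 and 9 are headed as apparent clearance, but their endpoint and analysis lines say only clearance. Outcomes 10 and 11 speak of volume of distribution with no qualifier. The analysis line for artesunate clearance is "Mean Artesunate clearance (L/Kg/hr) will be compared to historical studies", the comparators are "IV, oral and rectal administration among adults following similar dosing", and the method is the "students t-test for one-sample observation and a p-value of 0.05 considered" significant. The plan gives no estimate of F, names no reference study or value, and describes no dose adjustment.

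The IV background in section 1.3 gives artesunate "with an observed clearance range of 2-3 L/kg/hr and a volume range of 0.1-0.3 L/kg". The IV AUCs quoted there all come from 120 mg; for DHA, "The AUC of DHA following IV administration of 120 mg AS in adults ranged from 1850 ng*hr/ml in healthy volunteers". The study dose is 200 mg. Sections 1.6 and 5.4 predict minimal systemic absorption from the vaginal route.

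**The concern.** After an extravascular dose, dose divided by AUC gives CL/F. After an IV dose it gives CL. Testing one against the other mixes a difference in clearance with a difference in the fraction reaching the circulation, and the planned analysis has nothing to separate them.

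The protocol implicitly recognises this. Section 1.3 explains that IM clearance and volume resembled IV values because IM bioavailability is high (above 86%). It expects the reverse for vaginal dosing. A table reporting significantly higher clearance and volume than IV could then be read as altered disposition of artesunate and DHA, when the only finding is low F. Section 4.8 says the results go to the Ministry of Health to inform questions about systemic exposure and malaria resistance, so the label on that finding matters.

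**Working it through.** **Inputs.** All from section 1.3, healthy adults:
- artesunate AUC (ng·h/mL): IV 120 mg, 876; rectal 200 mg, 796; oral 200 mg, 67
- DHA AUC (ng·h/mL): IV 120 mg, 1850; rectal 200 mg, 965; oral 200 mg, 1158
- rectal artesunate half-life 0.95 h

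Body weight is at least 50 kg (section 4.3); a mean of 50 to 70 kg is assumed where weight is needed. The number evaluable is 12. The plan gives no SD or effect size, so CVs of 30, 50 and 80% are assumed, with a two-sided test because sidedness is not stated.

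**Check on the protocol's own figures.** CL = dose/AUC = 120/0.876 = 137 L/h, which is 2.74 L/kg/h at 50 kg and 2.28 at 60 kg, inside the quoted IV range of 2 to 3 (1.96 at 70 kg). The formula and the inputs agree with the protocol.

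**Ratio to IV.** With equal true clearance, (CL/F)/CL = 1/F.
- Artesunate rectal: 200/0.796 = 251 L/h; 251/137 = 1.8.
- Artesunate oral: 200/0.067 = 2985 L/h; 2985/137 = 22.
- DHA IV: 120/1.850 = 64.9 L/h. Rectal: 200/0.965 = 207 L/h, ratio 3.2. Oral: 200/1.158 = 173 L/h, ratio 2.7.

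These L/h ratios need no body weight. For DHA, a common conversion factor from artesunate cancels. None of them requires true clearance to differ between routes. They use dose over mean AUC, so they indicate size and are not exact means of individual values.

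**Volume.** Rectal V/F = (CL/F) × half-life/ln 2 = 251 × 0.95/0.693 = 344 L, or 4.9 to 6.9 L/kg at 70 to 50 kg. The quoted IV volume is 0.1 to 0.3 L/kg, so the ratio runs from 4.9/0.3 = 16 to 6.9/0.1 = 69. F explains only a factor of 1.8. The rest goes with the longer terminal half-life, which section 1.3 says "may reflect absorption rate-limited elimination of AS". If the terminal slope is absorption, V/F is inflated beyond 1/F.

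**Chance of a significant result with equal true clearance.** This is a one-sample t-test, n = 12, against a fixed IV value, with noncentrality √12 × (1 − F)/CV. Probability of declaring CL/F higher than IV CL:

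| F | CV 30% | CV 50% | CV 80% |
|---|---|---|---|
| 0.8 | 56% | 24% | 12% |
| 0.545 (rectal artesunate: 137/251) | 99.7% | 82% | 44% |
| 0.3 | 100% | 99% | 79% |
| 0.1 | 100% | 100% | 94% |

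A log-normal simulation gave the same pattern (F = 0.3: 100%, 100%, 96%).

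**Limit at very low F.** The artesunate quantification limit of about 80 nM (section 4.4, specimens) is 80 × 384.4/1000 = 30.8 ng/mL. Assuming the rectal Cmax/AUC ratio, 448.5/796 = 0.563 per hour, a Cmax at that limit implies an AUC of about 55 ng·h/mL. Against 876 × 200/120 = 1460, that is F of about 0.04. Below it, artesunate CL/F could not be estimated.

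**Dose normalisation of AUC (separate point).** Against a 120 mg IV reference, and assuming dose proportionality, the raw AUC ratio is F × 200/120 = 1.67F. For DHA, 1850 × 200/120 = 3083. The rectal AUC of 965 is 965/1850 = 52% of IV raw and 965/3083 = 31% normalised. At F = 0.6 the raw ratio is 1.0 and incomplete absorption cannot be seen.

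**The case against.** The headings of outcomes 8 and 9 do say apparent, section 2.2 uses /F throughout, and nothing states that a difference will be read as a change in physiological clearance. That is fair, but it does not cure the test: IV remains a named comparator with no allowance for F, and the volume headings carry no qualifier.

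The oral artesunate ratio of 22 should not be taken as absorption alone. Section 1.3 attributes the oral pattern to first-pass or systemic metabolism to DHA, and the DHA ratio is only 2.7. Section 1.3 also quotes an oral artesunate AUC of 119, which gives (200/0.119)/137 = 12. This stands: the ratio measures bioavailability including first-pass conversion. It still does not measure clearance.

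A reader might infer that the plan tests AUC and Cmax against 120 mg IV values. It does not. It asks for similar dosing and names no study; 120 mg is attached only to background IV AUCs; the IV Cmax is quoted without a dose; and the reference list includes an IV study at 2, 4 and 8 mg/kg. A reader might also infer that omitting dose normalisation produces faster clearance. It cannot, because clearance already divides by dose. The omission acts on exposure, and upwards. Finally, raw AUC at the studied regimen is a legitimate quantity for the resistance question, so a normalised ratio should be added and should not replace it.

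**Conclusion.** The point holds for the IV comparison in outcomes 8 to 11 and for nothing wider in those outcomes: oral and rectal values are themselves CL/F and V/F. On the protocol's own data, apparent clearance after other non-IV routes is 1.8 to 22 times IV for artesunate and 2.7 to 3.2 times for DHA, with no need for a difference in true clearance. V/F may be further off if the terminal slope reflects absorption, which section 1.3 raises only as a possibility and only for rectal artesunate.

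It would be tempting to say that a significant result is certain. The documents do not support that. At F = 0.8 the probability is at most about 56%, and below F of about 0.04 artesunate CL/F may not be estimable. At the low but measurable absorption between these, significance is likely.

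The figures assume clearance is constant between 120 and 200 mg, comparable healthy adults across studies, and the stated CVs. For DHA, treating IV artesunate as F = 1 rests on the protocol's assumption of complete conversion. The AUC point is lesser and conditional on a 120 mg IV study being chosen.

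**What to change.** In section 4.5.2:
- Remove IV from the comparators for outcomes 8 to 11, both analytes.
- Label all four endpoints as CL/F or V/F in the heading, endpoint and analysis lines.
- Compare them only with oral and rectal CL/F and V/F, and note that V/F is interpretable only if the terminal slope is elimination.
- Name each reference study with its route, dose and value.
- If the IV reference for AUC was given at a dose other than 200 mg, report the dose-normalised AUC ratio to IV beside the raw comparison and state the dose-proportionality assumption. Apply the same to Cmax only once the IV dose behind the reference value is identified.

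This needs no new data, samples or participants. The cost is a wording change, a small amount of extra analysis and one explicit assumption.
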